**Table 4-3: Date of Event or Censoring for Duration of Lower GI Response**

Situation	Date of event or censoring	Outcome	Event Description or Censoring Reason
Lower GI MAGIC score SD/PD before additional systemic therapy for aGVHD	First MAGIC assessment showing SD or PD, whichever occurs first	Event	SD/PD
Death without Lower GI MAGIC score SD/PD and not receiving additional systemic therapy for aGVHD	Date of death	Event	Death
Missing lower GI MAGIC assessment	Date of last evaluable MAGIC assessment before the first missed visit	Event	Missing visit
Additional systemic therapy for aGVHD used for any earlier progression, mixed response or stable aGVHD.	Date of last evaluable MAGIC assessment before additional systemic therapy for aGVHD	Event	Treatment Failure
Alive and without: Lower GI MAGIC score SD/PD, or missing, or initiation of additional systemic therapy for aGVHD	Date of last evaluable MAGIC assessment	Censored	Clinical cut-off date

Duration of Lower GI response will be summarized using Kaplan-Meier estimator. The number and percentage of subjects experiencing an event, and subjects censored will be summarized by apraglutide dose levels and in total. The median time-to-event will be presented where possible, along with the range and the associated two-sided 95% Brookmeyer-Crowley confidence interval. The event-free rate with 95% CI using Greenwood's formula will be provided for selected time points (e.g., 1, 3, 6, 12 and 24 months). Plots of the Kaplan-Meier estimate for the duration of Lower GI response will be presented by apraglutide dose levels and in total.

4.3.9.8 *Time to partial and complete lower GI-aGVHD response as defined by the MAGIC score*

Time to partial lower GI-aGVHD response is defined as the time from the first injection of apraglutide to the first partial response lower GI assessment according to MAGIC score. This is only defined for subjects with partial response. The ICE events and strategies defined in section 4.3.9.2 will be applied consistently for the estimation of CR and PR.

Time to complete lower GI-aGVHD response is defined as the time from the first injection of apaglutide to first complete response lower GI assessment according to the MAGIC score. This is only defined for subjects with complete response.

The time to partial or complete lower GI-aGVHD response will be summarized by apaglutide dose levels and in total using descriptive statistics including number and percentage of subjects with partial and complete response, the arithmetic mean, standard deviation (sd), median, first and third quartiles (Q1, Q3), minimum, and maximum.

*4.3.9.9 Duration of response from Day 28 or Day 56 on the total MAGIC score*

Duration of response from Day 28 (resp. 56) on the total MAGIC score is defined as the interval from the Day 28 (resp. 56) response (PR and CR) to death or new systemic therapy for aGVHD (including an increase in steroids >2 mg/kg/day MP equivalent), whichever occurs first, with at least 182 days of follow-up. This is only defined for subjects with partial or complete response at Day 28 (resp. 56).

Subject for which neither "new systemic therapy for aGVHD" or "dead" event occurs will be right censored at their last follow-up visit.

Duration of response from Day 28 (resp. 56) on the total MAGIC will be summarized using Kaplan-Meier estimator. The number and percentage of subjects experiencing an event, and subjects censored will be summarized by apaglutide dose levels and in total. The median time-to-event will be presented where possible, along with the range and the associated two-sided 95% Brookmeyer-Crowley confidence interval. The event-free rate with 95% CI using Greenwood's formula will be provided for selected time points (e.g., 1, 3, 6, 12 and 24 months). Plots of the Kaplan-Meier estimate for the duration of response will be presented by apaglutide dose levels and in total.

*4.3.9.10 Best Overall Response Rate By Day 91*

The best overall MAGIC score is defined as the best response recorded from the start of the treatment until either Day 91 or the start of additional systemic therapy for GI-aGVHD, whichever occurs first, with the following ranking between scores from best to worst: CR, PR, SD, MR, PD, "Other" (includes: Death, Treatment Failure, Missing).

The best overall Lower GI Response is defined as the best response recorded from the start of the treatment until either Day 91 or the start of additional systemic therapy for GI-aGVHD, whichever occurs first, with the following ranking between scores from best to worst: CR, PR, SD, PD, "Other" (includes: Death, Treatment Failure, Missing).

Subjects achieved best Overall Response (OR) if their best overall score is either PR or CR, that is if they achieve either PR or CR at any time point from the start of the treatment up to Day 91 and before the start of additional systemic therapy for GI-aGVHD.

The rate of Best Overall Response (BOR) is defined as the proportion of subjects who achieved OR.

The number and percentage of subjects by best total MAGIC score and by best overall Lower GI Response will be provided by apaglutide dose levels and in total.

In addition, the rate of Best overall Lower GI Response and Best Overall Response per Total MAGIC Score, along with the two-sided 95% confidence intervals using Clopper-Pearson exact method will be provided by apaglutide dose levels and in total.

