#### 4.3.9 Secondary Endpoints

This SAP will follow the estimand framework outlined in the ICH-E9(R1) addendum (FDA 2019) for the definition of the analysis of key secondary efficacy endpoint: Overall response on the lower GI according to MAGIC assessment.

Missing data:

- The general approach is that subjects with missing data or invalid such that the response cannot be determined will be included in the analysis as non-responders.
- Lost on follow-up: subject included but response data are missing and will be imputed as non-responder until the clinical cut-off date.
- Trial discontinuation: subject included but response data are missing and will be imputed as non-responder until the clinical cut-off date.

Censored data:

- At the time of the analysis, subject visits not yet completed and with expected date beyond the clinical cut-off date will be indicated as censored (e.g. a subject visit expected 7 days after the clinical cut-off date will be censored; for subjects deceased prior the clinical cut-off date, visits that would have occurred after the clinical cut-off date will be censored).
- If the subject scheduled visit is not expected to be completed, the visit is censored (e.g. scheduled subject visit week 12 prior the clinical cut-off but excluded for the subject who did not enter treatment extension period due to complete responder status at week 8; scheduled visit at week 11 for a subject who did not enter treatment extension period due to death at week 5).
- For all enrolled subjects, all visits covering the initial treatment phase (week 1 to 8 included) and all follow-up visits are expected to be completed.
- A censored subject visit does not contribute to the denominator of the visit.
- Across all scheduled visits, the denominator plus the number of censored subjects is constant and equal to the number of subjects in the analysis set (and treatment group when applicable).

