#### **Overall Response Rate at Day 56 on the Lower GI MAGIC Score**

The key secondary objective listed in protocol is to evaluate the overall response rate (partial response [PR] and complete response [CR]) at Day 56 on the Lower GI MAGIC score in subjects with SR lower GI-aGVHD Grade II to IV MAGIC that are treated with apraglutide, SS, and RUX.

To assess the key secondary objective, the key secondary efficacy estimand is defined by the following key attributes, according to the framework provided in ICH E9(R1) (FDA 2021):

- **Treatment:** weekly subcutaneous administration of low, or high, or low body weight dose of apraglutide on top of ruxolitinib within 72 hours prior the first administration of apraglutide excluding the use of additional systemic therapy from first administration of apraglutide.
- **Population:** Subjects with SR lower GI-aGVHD.
- **Population-level summary:** the proportion of subjects achieving overall response (CR+PR) on the Lower GI MAGIC score.
- **Variable:** Overall response on the Lower GI MAGIC Score.
- **Analysis Model:** use of FAS subjects for calculation of the proportion of overall response (CR and PR) on the Lower GI MAGIC score at Day 56 with a two-sided 95% confidence interval using Clopper-Pearson exact method.
- **Intercurrent events and strategy:**

- Terminal events:
  - ICE1: as death precludes further observations, based on composite strategy, assumes non-response from death event until the Primary Analysis clinical cut-off date included.
- Treatment change:
  - ICE2: in the event of treatment discontinuation, following treatment policy strategy; if a subject withdraws from treatment, observed values will be used regardless of the ICE.
  - ICE3: in the event of pausing or dose reduction of apaglutide, following treatment policy strategy, observed values will be used regardless of the ICE.
- Additional / alternative treatment:
  - ICE4: when additional systemic therapies are used for any earlier progression, mixed response or stable aGVHD, following hypothetical strategy, observed data will be discarded, and from the point of ICE, subjects will be considered as non-responder, as if treatment failure, until the Primary Analysis clinical cut-off date included.
  - ICE5: when a subject receives Donor Lymphocyte Infusions or Stem cell boost as concomitant medication or procedures, as per “treatment policy” strategy, all observed values will be used regardless of the ICE.

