*4.3.9.6 Durable overall response on the Total MAGIC Score from Day 56 to Day 91*

Durable overall response rate from Day 56 to Day 91 on the Total MAGIC Score is defined as proportion of subjects who had a response (either CR responder or PR responder) on the total MAGIC score at Day 56 and remain a CR responder or PR responder on the total MAGIC score at Day 91.

Percentage is computed using the number of subjects in treatment group as denominator.

The analysis of the durable overall response rate from Day 56 to Day 91 on the Total MAGIC Score will be performed similarly to the analysis of durable overall response on the Lower GI MAGIC score described in Section 4.3.9.5.

*4.3.9.7 Individual duration of lower GI response*

Duration of lower GI response is defined as the duration from the first date a subject is identified as a Lower GI MAGIC Score CR or PR responder until the next date a subject is Lower GI MAGIC Score SD/PD (i.e., return to baseline or worsening), or dead, whichever occurs first.

This is only defined for subjects with partial response or complete response. The best response is derived from assessments performed from the start of the treatment up to Day 91 or the start of additional systemic therapy for GI-aGVHD, whichever occurs first.

Subject for which neither “return to baseline or worsening” or “dead” event occurs will be right censored at their last MAGIC assessment visit. The ICE events and strategies defined in section 4.3.9.2. will be applied consistently for the estimation of CR and PR.

The event or censoring date will be determined based on the conventions listed in Table 4-3.

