#### *4.3.9.14 Failure-free survival up to 2 years post-first dose of apraglutide*

The failure-free survival time is defined as the time from the date of the first dose to the date of hematologic malignancy relapse/progression, non-relapse mortality, or the start of additional systemic therapy for GI-aGVHD, whichever occurs first.

The failure-free survival will be summarized using Kaplan-Meier estimator. The number and percentage of subjects experiencing an event, and subjects censored will be summarized by apraglutide dose levels and in total. The median time-to-event will be presented where possible, along with the range and the associated two-sided 95% Brookmeyer-Crowley confidence interval. The event-free rate with 95% CI using Greenwood’s formula will be provided for selected time points (e.g., 1, 3, 6, 12 and 24 months).

Subject for which neither “new systemic therapy for aGVHD”, “hematologic malignancy relapse/progression” or “non-relapse mortality” event occurs will be right censored at their last follow-up visit.

Plots of the Kaplan-Meier estimate for the failure-free survival will be presented by apraglutide dose levels and in total.

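### Table 4-3 of the SAP counts one missed lower GI MAGIC visit as loss of response, dated before the miss, which contradicts the text of 4.3.9.7 and shortens duration of response

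*SAP*

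**What the plan says.** SAP 4.3.9.7 defines duration of lower GI response as running from the first CR or PR to the next SD/PD assessment or death. A subject for whom neither "event occurs will be right censored at their last MAGIC assessment visit". The section then refers to Table 4-3 for event and censoring dates. The rows of the table that matter here are:

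- SD/PD before additional systemic therapy: an event, dated at "First MAGIC assessment showing SD or PD, whichever occurs first".
- Missing lower GI MAGIC assessment: an event described as a missing visit, dated "Date of last evaluable MAGIC assessment before the first missed visit". No minimum number of consecutive misses is set.
- Additional systemic therapy for aGVHD: an event, dated "Date of last evaluable MAGIC assessment before additional systemic therapy for aGVHD".
- Censoring, open only to a subject who is "Alive and without: Lower GI MAGIC score SD/PD, or missing, or initiation of additional systemic therapy for aGVHD".

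Protocol 1.5.2.2 counts the endpoint from first response until return to baseline or worse. SAP section 6, which lists changes from the protocol, does not mention a missed-visit event.

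**The concern.** The text and the table give the same subject different outcomes. A responder who misses one visit and is in response at all later ones is censored late under the text and is an early failure under the table. Two programmers could follow the SAP and draw different curves.

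The endpoint is reported as Kaplan-Meier medians and event-free rates at 1 to 24 months. Under the table those figures partly measure attendance. Exposure to a false event also depends on treatment path, because subjects treated longer have more scheduled MAGIC assessments to miss.

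Three further gaps lie in the same rules:

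- **Row order.** A subject who misses Week 17 and shows progression at Week 21 fits both the SD/PD row and the missing row. The table gives no precedence.
- **Treatment-failure date.** The table moves the failure back to the previous MAGIC visit. Under ICE4 in SAP 4.3.9.2, "from the point of ICE, subjects will be considered as non-responder". Failure-free survival (4.3.9.14) counts to relapse, non-relapse mortality "or the start of additional systemic therapy for GI-aGVHD, whichever occurs first".
- **What counts as missed.** After early treatment discontinuation, SAP 2.1 sends subjects to an early discontinuation visit and then to Weeks 26, 52 and 104. SAP 4.3.9 says "If the subject scheduled visit is not expected to be completed, the visit is censored", but also treats all follow-up visits as expected for every enrolled subject.

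What is at stake is the description of durability, a secondary endpoint. The primary safety objective is not affected.

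**Working it through.** The plan gives no figure for this endpoint, so there is none to reproduce. The check compares the two rules.

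**One subject.** First response at Week 2 (Day 14), Week 5 missed, in response at every later visit to Week 26 (Day 182).

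- Table 4-3: event at Week 4, duration 28 − 14 = 14 days.
- Text: censored at Week 26, duration 182 − 14 = 168 days.

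**Direction.** The table dates the failure at an assessment before the miss, when the subject was still in response. That date is never later than the date under the text, and it precedes any real loss. Subjects censored under the text can become events under the table, but not the reverse. The table's curve therefore cannot lie above the text's curve.

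**Number of visits.** From the schedule of assessments (SAP Tables B1 and B2), for a first response at Day 28, the MAGIC visits up to Day 182 are:

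- CR at Week 8: Days 35, 42, 49, 56, 91, 119, 147 and 182, so n = 8.
- Treated to Week 12: add Weeks 9 to 12, so n = 12.
- Optional treatment to Week 25: add also Weeks 14–16, 18–20 and 22–25, so n = 12 + 10 = 22.

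**False event in a continuing responder.** The per-visit miss rate q is an assumption, and misses are taken as independent. The probability is 1 − (1 − q)^n; for example, 1 − 0.95^8 = 0.337.

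| n | q = 1% | 2% | 5% | 10% |
|---|---|---|---|---|
| 8 | 0.077 | 0.149 | 0.337 | 0.570 |
| 12 | 0.114 | 0.215 | 0.460 | 0.718 |
| 22 | 0.198 | 0.359 | 0.676 | 0.902 |

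**Event-free rate at Day 182 under the table (n = 8).** With true rate S (assumed), the estimate is S(1 − q)^8; for example, 0.7 × 0.95^8 = 0.464.

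| S | q = 1% | 2% | 5% | 10% |
|---|---|---|---|---|
| 0.50 | 0.461 | 0.425 | 0.332 | 0.215 |
| 0.70 | 0.646 | 0.596 | 0.464 | 0.301 |

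**Share of events that are missed visits (n = 8).** This assumes a constant hazard over Days 28–182, with true losses detected at visits and the first event counted. Write S(t) for the true event-free probability. At visit j, the missed-visit probability is S(t_{j−1})(1 − q)^{j−1}q and the SD/PD probability is [S(t_{j−1}) − S(t_j)](1 − q)^j. Summed over the eight visits with S = 0.50 and q = 5%, these are 0.287 and 0.381, a share of 0.287/0.668 = 0.43.

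| S | q = 1% | 2% | 5% | 10% |
|---|---|---|---|---|
| 0.50 | 0.12 | 0.22 | 0.43 | 0.63 |
| 0.70 | 0.20 | 0.34 | 0.58 | 0.76 |

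**Simulation.** 200,000 responders on visits at Weeks 1–8, 13, 17, 21, 26, 52 and 104, with first response at Week 2, 3 or 4, exponential duration, independent misses and no deaths. Each cell is table versus text, 182 days after first response.

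| True median (assumed) | 2% missed | 5% | 10% |
|---|---|---|---|
| 90 days | 0.24 v 0.29 | 0.17 v 0.29 | 0.10 v 0.30 |
| 180 days | 0.44 v 0.54 | 0.32 v 0.54 | 0.19 v 0.55 |
| 365 days | 0.60 v 0.74 | 0.44 v 0.74 | 0.26 v 0.74 |

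At a true median of 180 days the rate with nothing missed is 0.538, so the text rule is nearly unaffected by independent misses. At 5% missed, about 5% of responders receive a duration of zero because the visit just after their first response was the one missed.

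**The case against.** The best defence is that the row is a deliberate conservative rule. The protocol leaves missing-data handling to the SAP (section 7.3). SAP 4.3.9 counts missing response data as non-response, and 4.3.9.7 applies the conventions of 4.3.9.2 to CR and PR. The text also hands dating to Table 4-3, so a programmer would probably follow the table. Patients may miss visits because they are deteriorating, in which case censoring biases duration long.

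Part of this stands. Because missing-data rules are delegated to the SAP, the silence of section 6 is weak evidence on its own, and informative misses are a reason to keep the rule as a sensitivity analysis. The rest does not. SAP 4.3.9.2 applies missing as non-response to response-rate calculation, and 4.1.2 says censoring is described separately for each time-to-event endpoint. Non-response at a missed visit would not justify a date before that visit, nor override a later visit showing response.

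On the further gaps, dating treatment failure at the previous assessment can be defended as a convention, and failure-free survival is a different endpoint. The sentence on expected follow-up visits can be read as each subject's own schedule. Both need clarifying but are secondary.

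The magnitude is illustrative. One miss rate is applied to dosing and follow-up visits alike. The 22-visit path requires a responder without CR up to Week 25. At 1–2% missed the shift is about 4 to 10 points, no larger than the binomial standard error of some 10 to 13 points for an assumed 15 to 20 responders. That comparison limits the consequence, but the shift is systematic and avoidable. The endpoint is descriptive, and the table labels missed-visit events separately.

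**Conclusion.** The concern holds and should be fixed. Table 4-3 and the text of 4.3.9.7 disagree, and the table turns a continuing responder with one missed visit into a failure dated before the miss. Relative to the text rule the direction is certain and needs no assumption about the miss rate. The size rests on assumed, independent miss rates: on the shortest path, a false-event probability of 8% at 1% missed, rising to 57% at 10%. From about 5% missed, roughly half of all events would be missed visits. If misses reflect deterioration, the text rule may err in the other direction.

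**What to change.** Revise Table 4-3 and the text of 4.3.9.7 so that they agree:

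- A missed visit followed by an assessment still in response is not an event.
- A subject without SD/PD, death or additional systemic therapy is censored at the last evaluable MAGIC assessment.
- Treatment failure is named as an event in the text and dated at the start of the additional systemic therapy.
- The table states which row applies when two fit.
- Visits not scheduled for a subject, such as Weeks 13 to 21 after early treatment discontinuation, are not missed. The two sentences in SAP 4.3.9 are reconciled accordingly.
- The present missed-visit-as-event rule is kept as a labelled worst-case sensitivity analysis.

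The cost is SAP wording, one derivation and one sensitivity table, with no new data. The downside is that censoring can lengthen the estimate if misses are informative; the sensitivity analysis would show by how much.
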